# Secondary Outcomes

As indicators of inflammation, the values of hypersensitive C-reactive protein

(hs-CRP), procalcitonin (PCT), and the neutrophil-to-lymphocyte ratio (NLR) also were recorded on postoperative days 1 and 2.

HR and mean arterial pressure (MAP) values were recorded at the following time points: operating room entry (T1), immediately before skin incision (T2), 1 min after skin incision (T3), skin suture (T4), and 30 min after extubation (T5). The requirement of supplemental analgesia was noted within 48 h postoperatively, along with the number of times patients got out of bed to perform activities within 48 h postoperatively and the distance walked after the patient's first attempt to get out of bed. Any occurrence of adverse reactions such as nausea, vomiting, and arrhythmia within 48 h postoperatively also was recorded. Any drug-related nerve damage after surgery was noted. Nerve deficits were defined according to sensory findings: 0—no nerve damage, 1—minor sensory paresthesia, 2—complete sensory parasthesia, 3—complete motor defect with or without sensory paresthesia, and 4—complex regional pain syndrome. Two researchers who were blinded to the group allocation assessed these outcomes.

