# Study Protocol and Statistical Analysis Plan

Official title: Analgesic Effect of Ropivacaine Combined with Methylene Blue in Fascia Iliaca Block for Patients

Undergoing Hip Arthroplasty

NCT number: NCT06284941

Date: December 24, 2024

For inclusion in this study, patients of either sex had to meet the requirements for hip replacement surgery, be in the age range of 65–85 years, have a body mass index (BMI) in the range of 18–28 kg/m², be categorized as American Society of Anesthesiologists (ASA) grade II to III, have no history of analgesic or local anesthetic allergies, and have no history of alcoholism or narcotic drug abuse. Patients were excluded if they met any of the following criteria: refusal by patient or family member to participate in the study, having a serious mental illness or inability to communicate clearly with researchers, severe coagulopathy, allergy to local anesthetics, severe psychiatric illness or other communication disorder, history of neurological disease such as Guillain-Barré syndrome, infection at the puncture site, delay in awakening post-surgery for more than 60 min, post-surgical use of an analgesic pump, and inability to follow-up at the required time points.

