### Randomization and Blinding

Using a computer-generated random sequence, a person who was not involved in the experimental operation divided the patients into two groups in which FICB was achieved with either methylene blue and ropivacaine (MB+R group) or ropivacaine only (R group). All serial numbers were encoded sequentially, kept, and scheduled for each experiment by someone other than the researcher. Because methylene blue is a blue liquid, exposure to the color could expose the experimental group. Thus, blinding was achieved by having different researchers perform different steps in the study to avoid the color affecting the experiment. The steps of the experimental procedure,

including the extraction of the liquid medicine, performance of the nerve block, and postoperative follow-up, were performed by different anesthesiologists, who were only responsible for independent experimental procedures, did not know the information about the patient outside the experiment, and did not communicate with each other about the patient and the experiment. Catheterization was not performed for any patient to prevent the color of the urine from exposing the experimental group.

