
### Study Outcomes

# Primary Outcomes

As a measure of pain, Visual Analog Scale (VAS) scores at both rest and with activity (passive straight leg raise at 45°) were recorded at the following time points: before block and at 2, 6, 12, 24, and 48 h postoperatively. The VAS score is a common way to assess pain using a sliding ruler about 10 cm long, marked with 10 scales on one side and "0" and "10" at each end. A score of 0 indicates no pain; a score of 10 indicates the most severe pain that is unbearable. The higher the score, the greater the degree of pain. In this study, a dedicated anesthesiologist assessed the pain of each included participant at different time points before and after surgery.

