#### Statistical Methods

SPSS 25.0 software was used for statistical analysis. Normally distributed data were expressed as mean  $\pm$  SD, and group comparisons were performed using independent samples t-test. Data with a skewed distribution were expressed as median (M) and interquartile range (IQR), and non-parametric tests were used for comparisons. Friedman's test was used for intra-group comparisons. Count data were expressed as

number (%), and comparisons between groups were performed using the  $\chi^2$  test. P<0.05 was considered statistically significant.

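### Times out of bed and distance walked are compared unadjusted with no preoperative walking measure described, so precision may be lost on these two secondary outcomes

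*Combined protocol and SAP*

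**What the plan says.** All references are to the combined protocol and SAP.

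- **Outcomes (Secondary Outcomes).** Two mobility measures are recorded: "the number of times patients got out of bed to perform activities within 48 h postoperatively and the distance walked". The distance is the one covered when the patient first gets up. Both are postoperative only.
- **Eligibility (opening section).** The criteria begin "patients of either sex had to meet the requirements for hip replacement surgery, be in the age range of 65–85 years", and go on to BMI 18–28 kg/m², ASA grade II–III, allergies and substance misuse. No inclusion or exclusion criterion refers to walking ability, walking aids or the reason for the hip replacement.
- **Baseline.** VAS pain is scored "before block and at 2, 6, 12, 24, and 48 h postoperatively" (Primary Outcomes). The activity score uses a passive leg raise, so it does not measure walking. No preoperative value is given for either mobility outcome.
- **Allocation (Randomization and Blinding).** "Using a computer-generated random sequence, a person who was not involved in the experimental operation divided the patients into two groups". No stratification is described.
- **Analysis (Statistical Methods).** For normal data, "group comparisons were performed using independent samples t-test"; for skewed data, "non-parametric tests were used for comparisons"; for count data shown as number and percentage, a chi-square test. The threshold is "P<0.05 was considered statistically significant". No covariate-adjusted or stratified analysis is mentioned.

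**The concern.** How often and how far a patient aged 65 to 85 walks in the first two days after hip replacement plausibly depends on how well that patient walked before. The criteria would let an independent walker and someone who could barely walk enter the same trial. As described, the plan does not restrict, measure, stratify by or adjust for that difference.

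Two things are at stake, both confined to the two mobility outcomes. First, between-patient variation that a baseline measure could explain stays in the error term, so a real mobility difference is harder to detect. Second, if one group happens to contain better walkers, nobody can see it in the baseline table or correct for it.

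**Working it through.** The documents state no sample size, power, effect size, SD or correlation, so there is no planned figure to reproduce. What follows shows the size of the effect under stated assumptions.

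**Inputs from the documents:** two randomised groups, unadjusted tests, alpha 0.05.

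**Assumptions not in the documents:** two-sided testing; 1:1 allocation; 30 to 60 patients per group; a true difference of 0.5 SD where power is shown; correlation r between preoperative walking and the mobility outcome, varied from 0.2 to 0.7.

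**1. Is the unadjusted comparison biased?** A simulation of 20,000 trials with 40 per group, normal outcomes and no true effect gave:

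| r | mean difference (SD) | type I error |
|---|---|---|
| 0.3 | −0.0003 | 0.051 |
| 0.5 | −0.0015 | 0.052 |
| 0.7 | −0.0006 | 0.052 |

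So there is no systematic bias, and the error rate is held.

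**2. How much precision is lost?** Linear adjustment multiplies the residual variance by 1 − r². Confidence interval width is multiplied by √(1 − r²). The unadjusted analysis needs 1/(1 − r²) times as many patients for equal precision.

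| r | 1 − r² | width ratio | patients needed, unadjusted / adjusted |
|---|---|---|---|
| 0.2 | 0.96 | 0.98 | 1.04 |
| 0.3 | 0.91 | 0.95 | 1.10 |
| 0.5 | 0.75 | 0.87 | 1.33 |
| 0.6 | 0.64 | 0.80 | 1.56 |
| 0.7 | 0.51 | 0.71 | 1.96 |

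For r from 0.3 to 0.6 this is 10% to 56% more patients. At r = 0.3 the interval narrows by 1 − 0.954 = 4.6%; at r = 0.2, by 2%.

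**3. What does that mean for power?** With 40 per group and a 0.5 SD difference, power is 0.61 unadjusted, against 0.65 (r = 0.3), 0.73 (r = 0.5) or 0.88 (r = 0.7) adjusted.

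**4. How likely is a chance imbalance?** The SD of the baseline difference between groups is √(2/n) in baseline SD units. At n = 40 it is √(2/40) = 0.224. The probability of a difference above 0.25 SD is 2 × [1 − Φ(0.25/0.224)] = 0.26. It is 0.33 at 30 per group and 0.17 at 60. An imbalance of exactly 0.25 SD shifts the expected outcome difference by r × 0.25, which is 0.075 SD at r = 0.3 and 0.15 SD at r = 0.6.

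**The case against.** The strongest reply is that an unadjusted comparison of a randomised secondary outcome is valid, and that a prognostic covariate could be suggested for almost any outcome in any trial. That is correct. It limits the point to an efficiency suggestion, but does not remove it, because a specific and inexpensive covariate is available for two named outcomes.

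Four stronger readings are tempting and are not supported:

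- A reader might infer that preoperative disability is being mistaken for a treatment effect. Under random allocation it adds noise and possible chance imbalance, not bias, and the 0.05 threshold already allows for chance imbalance on average. This assumes that the groups analysed are the groups randomised.
- A reader might infer that walking ability was never assessed. The document is short and has no list of baseline variables, so it supports only that no such measure is described.
- A reader might infer that VAS is the only assessment before the block. Age, BMI, ASA grade and screening for coagulopathy and neurological disease are also required. None of these is a walking measure, though some may exclude certain causes of immobility. Nothing shows how many patients with poor mobility were enrolled.
- A reader might take 10% to 56% as a property of this trial. It follows only from an assumed correlation and from linear adjustment of a continuous outcome. A four-level category or a stratified rank test on a skewed count or distance may recover less, and sparse strata can cost power in a small trial.

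The document is also written in the past tense. If data collection is over, a new baseline question cannot be asked. That limits when the fix can be made, but does not make the point wrong.

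**Conclusion.** The point holds as a cheap improvement. The two mobility outcomes have no described preoperative counterpart, eligibility leaves walking ability open, and the planned tests are unadjusted. The comparison remains unbiased. If prior walking ability predicts early mobility, some precision is given up and a chance imbalance stays invisible.

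The size depends on a correlation that the documents do not give. Over an assumed 0.3 to 0.6 with linear adjustment, the cost is equivalent to about 10% to 56% more patients; at 0.3 or below it is minor. Nothing here affects the primary VAS comparison.

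**What to change.** At the existing pre-block VAS assessment, record pre-admission walking ability in a few ordered categories, for example unaided, with an aid, indoors only, or unable. If enrolment is complete, take it from existing records where available. If it cannot be recovered, report its absence as a limitation when interpreting the mobility results. If it was collected but not described, say so and show it by group.

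Recording alone recovers no precision, so Statistical Methods also needs a sentence. It should name walking category as a covariate, or as the stratum in a stratified rank test if the data are skewed, for times out of bed and distance walked. It should also give a rule for merging sparse categories. Fix this before results by group are seen; otherwise label the adjusted analysis as post hoc and show it beside the unadjusted one.

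The cost is one extra question, or a records check, and a slightly longer analysis.

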#### **Operative Procedures**

Nerve Block

Before general anesthesia induction, FICB was performed under ultrasound guidance using the Edge II ultrasound device (Sonosite, USA). With the patient in supine position and the surgical area disinfected, the high-frequency ultrasound probe was placed perpendicular on the inguinal ligament. The probe was slowly moved until the "bowtie sign" created by the internal oblique and sartorius muscles was observed. This sign corresponds to the confluence of the fascia lata and fascia iliaca, which represents the fascia iliaca compartment. With an in-plane technique in the caudal to cranial direction, the needle tip was inserted deep to the fascia iliac. After confirming it could be withdrawn without blood, local anesthetic drugs in a volume of 30 ml were injected. Patients in the MB+R group received 0.25% ropivacaine (Product Batch Number: EE2344, Zhejiang Xianju Pharmaceutical Co., Ltd.) and 0.05% methylene blue (Product Batch Number: 2310032, Jichuan Pharmaceutical Group Co., Ltd.), and those in the R group received only 0.25% ropivacaine (same batch number).

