After successful nerve block, all patients were transferred to the operating room where they received routine monitoring of heart rate (HR), electrocardiogram (ECG), oxygen saturation (SpO2), etc. Radial artery puncture catheterization was performed under local anesthesia for invasive arterial pressure monitoring. For anesthesia induction, patients received an intravenous injection of propofol 1.0-2.0 mg/kg, rocuronium bromide 0.6 mg/kg, and sufentanil 0.2-0.3 µg/kg. The specifications of mechanical ventilation after endotracheal intubation were: tidal volume (VT) 6-8 ml/kg, respiratory rate (RR) 10–12 times/min, positive end expiratory pressure (PEEP) 3-5 cmH2O, and end-expiratory carbon dioxide partial pressure (PETCO2) 35~45 mmHg. Anesthesia was maintained by inhalation of 1.5%-2.0% sevoflurane along with intravenous infusion of remifentanil at 0.05-0.2 µg/kg/min and intermittent administration of rocuronium bromide 5-10 mg according to the intraoperative situation to maintain muscle relaxation. Blood pressure (BP) and HR fluctuation within 20% of baseline values was allowed according to the intraoperative situation. If BP dropped by >20% of the baseline value or if systolic BP was <90 mmHg, ephedrine 6 mg was given. If the HR was <50 beats/minute, an intravenous bolus of atropine 0.5 mg was given. All operations among included patients were performed by the same surgical team with the same surgical method, and the surgical method was hip replacement with posterolateral approach in the lateral decubitus position. The inhalation of sevoflurane and infusion of remifentanil was stopped 5 min before the end of the operation. After surgery, the patient was transferred to a recovery room, and

the endotracheal tube was removed once the patient was awake and spontaneous breathing had resumed. According to our pre-test experience, many patients refuse the use of analgesic pumps due to the relatively high cost, certain drug-related side effects, and the option of FICB. Thus, we did not include cases with post-surgical use of an analgesic pump in this study. In this study, fascia iliaca block was used to administer postoperative analgesia to patients. If the patients were not satisfied with the effect of fascia iliaca block, additional opioids were used for supplemental analgesia. At the same time, to avoid the effect of drugs on the level of patients' inflammatory factors, the use of non-steroidal analgesic drugs was prohibited.

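### Adverse reactions are counted only after surgery, although the study drug is injected before induction, so the safety comparison is incomplete from injection to end of surgery

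*Combined protocol and SAP*

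**What the plan says.** The Nerve Block part of Operative Procedures puts the randomised exposure before anaesthesia: "Before general anesthesia induction, FICB was performed under ultrasound guidance". It is a single administration ("local anesthetic drugs in a volume of 30 ml were injected"), and the arms differ only in whether methylene blue is added to the ropivacaine.

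Operative Procedures then continues: "After successful nerve block, all patients were transferred to the operating room where they received routine monitoring of heart rate (HR"; the sentence goes on to ECG and oxygen saturation. The arterial line, induction, intubation and the operation follow. The section also sets treatment triggers for low blood pressure and low heart rate, for example "If the HR was <50 beats/minute, an intravenous bolus of atropine 0.5 mg was given".

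Secondary Outcomes defines the safety outcomes:
- adverse reactions: "Any occurrence of adverse reactions such as nausea, vomiting, and arrhythmia within 48 h postoperatively also was recorded";
- nerve damage: "Any drug-related nerve damage after surgery was noted".

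The same section lists HR and MAP at five points: operating room entry (T1), just before incision (T2), 1 min after incision (T3), skin suture (T4) and 30 min after extubation (T5). Two researchers blinded to allocation assess these outcomes.

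Under Statistical Methods, counts are compared between groups with a chi-square test, and "P<0.05 was considered statistically significant".

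**The concern.** For a treatment given once, the natural origin for safety observation is the moment it is given. Here the window opens at a later surgical milestone. The period nearest to dosing falls outside the adverse-reaction outcome, even though arrhythmia, one of the plan's own examples, can occur in it and ECG is already being monitored for most of it.

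What remains in the window leans towards nausea and vomiting, to which the anaesthetic and opioids used in both arms can also contribute. Similar adverse-reaction rates in the two arms would then say little about reactions at injection or during the operation. Methylene blue is the added agent, so a reader would look to this outcome for evidence on its tolerability. The chi-square test cannot recover events that were not recorded.

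**Working it through.** No formula applies. The documents give no sample size, event rate, operating time or block-to-surgery interval, and the plan states no figure to reproduce. The check is to put the events in order and see which outcome covers each segment.

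1. **Injection to operating room entry.** The block is given before induction and before transfer. Routine monitoring is described only after transfer. No outcome covers this segment: T1 is taken on entry, after the block, and the adverse-reaction window has not opened.
2. **Operating room entry to end of surgery.** ECG, oxygen saturation and invasive arterial pressure are monitored. The only outcomes recorded are HR and MAP at T1 to T4, which is 2 variables × 4 times = 8 values per patient. An arrhythmia, an allergic-type reaction, or a hypotensive or bradycardic episode treated between two readings leaves no outcome record. The ephedrine and atropine triggers are stated, but neither the episodes nor the drug use is listed as an outcome.
3. **End of surgery to 48 h.** Adverse reactions are recorded, and T5 adds one further HR and MAP reading. Nerve damage is also dated after surgery, so it does not reach back into segments 1 and 2.

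**Does the 48 h phrase fix the start of the window or only its end?** Two features of the text favour a postoperative start. Secondary Outcomes uses the same phrase for supplemental analgesia and for getting out of bed, which can only begin after surgery. Where the plan wants an earlier time point it names one: the pre-block pain score under Primary Outcomes, and operating room entry for HR and MAP. No earlier start is named for adverse reactions.

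Segments 1 and 2 therefore have no adverse-event outcome, and segment 2 has partial haemodynamic coverage.

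**The case against.** The strongest reply has four parts.

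- **The patient is closely watched during the operation.** This is right, and HR and MAP at T1 to T4 do give a between-arm view of intraoperative haemodynamics. A reader might infer from the window that nothing is observed before the end of surgery, or that every acute reaction to methylene blue is lost. The documents do not support that. Monitoring is described, four readings are outcomes, and a reaction that starts or persists after surgery would still be counted. What the text supports is narrower: events in this period are not defined or captured as adverse events.
- **The wording may fix only the end of the window.** This is possible, but it is the weaker reading for the reasons in the check above. If it is what the sponsor meant, one sentence would settle it.
- **The gap may be short.** The documents give no duration. A reader might infer that the window opens hours after dosing, but that would be an assumption. The gap exists whatever its length.
- **Earlier events are harder to collect without bias.** This stands. Under Randomization and Blinding, drug preparation, block and follow-up are split between different anesthesiologists because methylene blue is visibly blue. Events at injection may be known only to staff who could see the colour, and no record covering the injection is described. Hypotension and bradycardia under general anaesthesia are also non-specific, as nausea and vomiting are.

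**Conclusion.** The point holds in a limited form. Adverse reactions are defined only for the 48 h after surgery, while the sole randomised exposure is injected before induction. Events from injection to end of surgery, including intraoperative arrhythmia, are not captured as adverse events, apart from HR and MAP at fixed times from operating room entry onward. For that period the safety comparison of MB+R with R is incomplete.

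Its size cannot be put as a number. Assuming rates for reactions confined to the uncounted period and then noting that none is recorded would be circular, and the documents give no rate to start from. Nor do they say how often, or when, acute reactions to methylene blue should be expected.

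The conclusion assumes that the adverse-reaction window begins after surgery, which is the plain reading. It concerns a secondary outcome and leaves the primary pain comparison untouched. It should be corrected because it bears on the safety of the added drug and the correction is inexpensive.

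**What to change.** In Secondary Outcomes, define the adverse-reaction window as running from the start of the block injection to 48 h after surgery. Report it by arm in two parts: injection to end of surgery, and end of surgery to 48 h.

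- **Intraoperative events.** Take arrhythmia, allergic-type reactions, and hypotension or bradycardia from the intraoperative monitoring and anaesthesia records. The thresholds already in Operative Procedures (BP more than 20% below baseline or systolic below 90 mmHg; HR below 50 beats/minute) can serve as event definitions only, with no change to management. The plan does not say which reading is the baseline BP, so the definition should name it.
- **Events at injection.** Take these from the block operator's note where one exists. If there is no record of that period, report the segment as a limitation.
- **Classification.** Have the blinded assessors classify events from records in which drug colour and allocation are masked.

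The cost is a revised sentence, record abstraction and masking, with no new visit or procedure for patients. Two downsides should be stated: more non-specific anaesthetic events will be counted in both arms, which is why the two parts should be kept separate, and events at injection may be reported by staff who could see the colour. The document is written in the past tense and gives drug batch numbers, so if the patients have already been treated, the change can be made only through retrospective abstraction or a stated limitation.

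### Nerve damage is recorded only if judged drug-related, with no assessment time and no grade for partial weakness, so real deficits can go uncounted

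*Combined protocol and SAP*

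**What the plan says.** All of this is in the Secondary Outcomes section of the combined protocol and SAP unless another section is named.

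- **What is counted.** "Any drug-related nerve damage after surgery was noted". No criteria for relatedness follow, and there is no instruction to record deficits put down to another cause.
- **When.** After surgery, with no hour, day or visit. The other secondary outcomes have days, named time points or a 48 h window. The exception is walking distance, which is tied to the first attempt to get out of bed. The general safety item, for example, reads "Any occurrence of adverse reactions such as nausea, vomiting, and arrhythmia within 48 h postoperatively also was recorded". The Primary Outcomes section schedules pain scores "before block and at 2, 6, 12, 24, and 48 h postoperatively", and no later contact is described.
- **How it is graded.** "Nerve deficits were defined according to sensory findings". Grades 1 and 2 are sensory. The next is "3—complete motor defect with or without sensory paresthesia", and grade 4 is a pain syndrome.
- **By whom.** "Two researchers who were blinded to the group allocation assessed these outcomes".
- **Analysis.** Statistical Methods gives a chi-square test for count data at P<0.05 and nothing specific to this scale.

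**The concern.** This is the only outcome devoted to neurological safety, in a trial of an agent injected beside nerves. Three features of the written rule weaken it.

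**Attribution.** Every patient has a needle block (Operative Procedures: "local anesthetic drugs in a volume of 30 ml were injected") and then hip replacement by a posterolateral approach. A deficit may come from the injected drug, the needle, the surgery or a block that has not worn off, and the plan gives the assessor no way to tell these apart. A blinded assessor does not even know which drug the patient received. The randomised comparison can supply attribution, because surgery and needle are common to both arms, but only if all deficits are counted.

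**Timing.** With no examination time, block-offset criterion or persistence rule, the text does not say how residual numbness is to be distinguished from injury. Grades 1 and 2 could describe either.

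**Scale.** A patient with partial weakness fits no grade, and a scale said to be sensory contains a motor grade and a pain syndrome.

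At stake is what a reported result would mean. A count of zero could mean that no deficits occurred, or that those seen were put down to surgery.

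**Working it through.** **Figures in the plan.** There are none to reproduce. The documents state no sample size, power or expected deficit rate. The timing and scale points rest on the text alone. The arithmetic below covers only the attribution condition, and all its inputs are assumptions.

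**Inputs.** n per arm: 40–50 for power, 30–100 for the check on single events. True deficit rates: 15% versus 3% for power, 5% and 10% for single events. Share *s* of true deficits judged drug-related, taken as equal in both arms: 1, 0.5 or 0.25. Significance level: 0.05 (Statistical Methods), taken as two-sided because the plan does not say.

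**Step 1: expected counts.** Recorded rate = *s* × true rate. With *s* = 0.5, 15% versus 3% becomes 7.5% versus 1.5%. The 5:1 ratio is kept, but the difference falls from 12 to 6 percentage points.

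- n = 40: 40×0.15 = 6.0 and 40×0.03 = 1.2 events become 3.0 and 0.6.
- n = 50: 50×0.15 = 7.5 and 50×0.03 = 1.5 events become 3.75 and 0.75.

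The pooled expected count per arm goes from (6.0+1.2)/2 = 3.6 to 1.8 at n = 40, and from (7.5+1.5)/2 = 4.5 to 2.25 at n = 50. These are small for a chi-square approximation, so Fisher's test is shown beside the plan's test.

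**Step 2: power.** This is the sum of binomial probabilities over all pairs of event counts for which the test gives P<0.05.

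| Test | n per arm | All deficits counted | Half counted |
|---|---|---|---|
| Chi-square, uncorrected | 40 | 53% | 22% |
| Chi-square, uncorrected | 50 | 58% | 28% |
| Fisher | 40 | 29% | 4.5% |
| Fisher | 50 | 40% | 9.2% |

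The direction is the same under both tests. The fall to near zero appears only under Fisher and partly reflects that test's conservatism at such low counts.

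**Step 3: chance of recording any deficit in one arm.** P(at least one) = 1 − (1 − *s*×*p*)^n. For example, *p* = 5%, *s* = 0.5 and n = 50 give 1 − 0.975^50 = 72%.

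| True rate | n | *s* = 1 | *s* = 0.5 | *s* = 0.25 |
|---|---|---|---|---|
| 5% | 30 | 79% | 53% | 31% |
| 5% | 50 | 92% | 72% | 47% |
| 5% | 100 | 99% | 92% | 72% |
| 10% | 30 | 96% | 79% | 53% |
| 10% | 50 | >99% | 92% | 72% |
| 10% | 100 | >99% | 99% | 92% |

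The loss is large for rare deficits in small arms and small for commoner deficits in arms of 100.

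**The case against.** **The assessors are blinded.** True, and the Randomization and Blinding section adds separation of roles and avoidance of catheterization. A reader might infer that attribution would differ by arm. The documents do not show that, and the calculation above assumes the same filter in both arms. Blinding does not, however, recover deficits put down to surgery, date the examination or grade partial weakness.

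**A good filter would help.** If assessors could correctly remove surgical deficits, the comparison would be cleaner. The plan gives them no criteria for doing so.

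**Deficits may be caught elsewhere.** The adverse-reaction item is an open list without the drug-related condition, and out-of-bed counts and walking distance carry some indirect motor information. This softens the point. But that item neither names nor grades nerve deficits, and mobility has many causes.

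**Injury and residual block.** A reader might infer that the plan cannot separate the two, or that methylene blue would look injurious by prolonging the block. The outcome is worded as damage, so an assessor may leave an expected residual block uncounted. The text supports only that no rule is written. Prolonging the block is not a stated purpose, and block duration is not given. With invented residual-block rates of 30% and 10% and 3% injury in both arms, graded deficits would be 1 − 0.97×0.70 = 32.1% versus 1 − 0.97×0.90 = 12.7%. Nothing in the documents supports those rates. That scenario also has assessors exercising no judgement, whereas the attribution scenario has them discarding half of what they see.

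**Zero events prove little in a small trial.** With none in 40–50 patients, 1 − 0.025^(1/n) still allows a true rate of 8.8% to 7.1%. That depends only on n and would be the same after the fix, so it is not evidence for this point.

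**Conclusion.** The point holds as a defect in the written rule. Only nerve damage judged drug-related is noted, without criteria or a time, on a scale with a gap at partial weakness. Followed as written, the rule drops deficits attributed to the needle or the surgery. This goes beyond missing detail.

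The size is illustrative. With 40–50 per arm, 15% versus 3%, and half of the deficits discarded equally in both arms, power falls by about 30 percentage points under the plan's test (53–58% to 22–28%) and from 29–40% to 5–9% under Fisher. The sample size, rates and discarded share are all assumed.

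A reader might go further and infer that harm was hidden. The documents do not show that any deficit was discarded, only that the rule permits it and would leave no trace. For one secondary safety outcome with blinded assessment, this should be corrected, but it does not bear on the primary pain comparison.

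**What to change.** 1. Delete the drug-related condition. Have the two blinded researchers record every sensory or motor deficit, whatever its presumed cause, in all randomised patients. That includes patients later removed under the criteria for delayed awakening or pump use.
2. Fix the time at the existing 48 h contact.
3. Beside the 0–4 grade, record any motor weakness (yes/no). Finer motor grading is for the investigators to choose.
4. Keep presumed causality as a separate descriptive field that does not decide what is counted.
5. Report counts and proportions by arm with exact 95% confidence intervals, labelled *residual block or deficit at 48 h*. Do not claim absence of lasting nerve damage from 48 h data.

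**Cost.** A wording change and a short sensory and motor check, with two added fields, at a contact already made. Surgical deficits will add background events in both arms. No baseline neurological examination is described, so the count cannot be called new deficits; deficits present beforehand would also fall in both arms. Residual block will still be counted at 48 h, which is why the label matters.

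The document is written in the past tense. If recording is already complete, the report should state when deficits were assessed and how relatedness was judged. It should also list by arm any deficits seen but not counted, and limit its safety claim accordingly.
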